7. DISCONTINUATION OF STUDY INTERVENTION AND PARTICIPANT DISCONTINUATION/WITHDRAWAL

7.1. Discontinuation of study intervention

Not applicable to this study.

7.2. Participant discontinuation/withdrawal from the study

A participant may withdraw from the study at any time at the participant's own request for any reason (or without providing any reason).

A participant may be withdrawn at any time at the discretion of the investigator for safety, behavioral, or compliance reasons.

Investigators will attempt to contact participants who do not return for scheduled visits or follow-up.

All data and samples collected up to and including the date of withdrawal of/last contact with the participant will be included in the study analyses. If the participant withdraws consent for disclosure of future information, the sponsor may retain and continue to use any data collected before such a withdrawal of consent.

If a participant withdraws from the study, the participant may request destruction of samples taken and not tested, and the investigator must document this in the site study records. Local regulations may also require that any samples taken and not yet tested at the time a participant withdraws from the study are destroyed.

A participant can also request for the destruction of their samples any time during the study. The investigator must document the request in the site study records.

The primary reason for participant discontinuation/ withdrawal from the study will be documented in the eCRF based on the list below:

Reasons	Additional items/Sub-reasons
AE	Unsolicited AE Solicited event SAEs/AESIs
Lost to follow-up	Unknown Other, Specify
Protocol deviation	

Reasons	Additional items/Sub-reasons
Investigator Decision	Specify
Pregnancy	
Site Terminated by Sponsor	
Study Terminated by Sponsor	
Withdrawal by Participant	Burden of Procedure Participant Relocated Pandemic Other, Specify
Death	
Other	Specify

Participants who are withdrawn from the study because of AEs/SAEs must be clearly distinguished from participants who are withdrawn for other reasons. Investigator will follow participants who are withdrawn from the study due to an AE/SAE/AESI until the event is resolved, stabilized, otherwise explained, or the participant is lost to follow up (see Section 10.3.5.5).

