The primary estimands address the objective of demonstrating the NI of the humoral immune response in non-immunocompromised adults aged 18-49 YOA AIR for RSV disease, when compared to older adults aged ≥ 60 YOA after administration of a single dose of RSVPreF3 OA investigational vaccine. This is done by estimating the true effect of the vaccine without any confounding of other medications/vaccinations/medical condition(s) on the target population since the impact of developing medical condition(s) forbidden by protocol and use of forbidden medications and vaccinations is anticipated to modify the vaccine effect.

Table 8 Secondary estimands for safety (Part A and Part B)

Treatment	Population	Endpoint (Variable)	Attributes		Summary measure	
			Intercurrent events (ICEs)			
			Description	Handling strategy		
RSVPreF3 OA investigational vaccine at Day 1.	Non-immunocompromised adults at increased risk for RSV disease with 18-49 YOA. OA with ≥ 60 YOA.	
 Occurrence of each solicited administration site event with onset within 4 days after study intervention administration. Occurrence of each solicited systemic event with onset within 4 days after study intervention administration. Occurrence of unsolicited AEs within 30 days after study intervention administration. Occurrence of SAEs (including fatal and related SAEs) and AESIs after study intervention administration (Day 1) up to study end (Month 6). 	Taking prohibited medication /vaccine or intercurrent medical condition during respective duration.	All the data collected for the variable of interest are used regardless of whether the intercurrent event occurs (treatment policy).	The percentage of participants by group who report each of the endpoints.	

AE=Adverse event; AESI=Adverse event of special interest; RSV=Respiratory syncytial virus; SAE=Serious adverse event; YOA=Years of age.

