9.5. Pre-dose sample size determination

The target sample size for the study is approximately 850 participants for Part A: 425 participants in Cohort 1 (RSV-A-AIR [18-49 YOA group]) and 425 participants in Cohort 2 (RSV-OA [≥ 60 YOA group]), to obtain at least 722 evaluable participants (361 participants in the RSV-A-AIR [18-49 YOA] cohort and 361 participants in the RSV-OA [≥ 60 YOA] cohort) for the evaluation of the primary objectives, assuming that approximately 15% of the enrolled participants will not be evaluable.

Participants who withdraw from the study will not be replaced.

The power to demonstrate the primary NI objectives following the hierarchical testing procedure described in Section 9.3.1 is presented in Table 20.

Table 20 Power for primary objectives of non-inferiority of the humoral immune response after RSVPreF3 OA vaccine between the RSV-A-AIR (18-49 YOA) Cohort 1 to RSV-OA (\geq 60 YOA) Cohort 2 for 361 evaluable participants per group

Objective	Standard deviation (SD) of log ₁₀ titers / SRR (%)	Non-inferiority margin	Type II Error	Power ¹
NI for RSV-A strain				
GMT RSV-A	SD=0.45	1.5	0.05	99.95%
SRR RSV-A	SRR=81.6% ²	10%	6.92	93.08%
Global power for RSV-A strain				93%
NI for RSV-B strain				
GMT RSV-B	SD=0.45	1.5	0.05	99.95%
SRR RSV-B	SRR=78.7% ²	10%	9.56	90.44%
If non-inferiority is demonstrated for RSV-A, global power for RSV-B strain				90%

NI=Non-inferiority; SRR=Seroresponse rate; GMT=Geometric mean titer; RSV=Respiratory syncytial virus

¹Pass 2019 1-sided alpha=2.5% for each endpoint (GMT ratio and SRR difference), two-Sample T-Tests for Non-Inferiority assuming equal variance for group GMT ratios and ^{CCI} for Non-Inferiority tests for group SRR difference, Non-inferiority limit=0.176 (=log₁₀(1.5)) for group GMT ratios

²Reference from RSV OA=ADJ-006

For the evaluation of reactogenicity and safety, the sample size of 1025 participants in combined Cohorts 1 and 3 (RSV-A-AIR group) has 64% and 87% probability of observing at least one vaccinated participant with AE if the true AE incidence rate is 0.1% and 0.2% respectively. This probability increases to at least 95% for true AE incidence rates \geq 0.3%.

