10.1.10. Study and site start and closure

Start of study and first act of recruitment

The start of study and the first act of recruitment are defined as FSFV at a country-level.

Study/Site Termination

GSK or designee reserves the right to close the study site or terminate the study at any time for any reason at the sole discretion of GSK. Study sites will be closed upon study completion. A study site is considered closed when all required documents and study supplies have been collected and a study-site closure visit has been performed.

The investigator may initiate study-site closure at any time, provided there is reasonable cause and sufficient notice is given in advance of the intended termination.

Reasons for the early closure of a study site by the sponsor or investigator may include but are not limited to:

For study termination:

- Discontinuation of further study intervention development

For site termination:

- Failure of the investigator to comply with the protocol, the requirements of the IRB/IEC or local health authorities, the sponsor's procedures, or GCP guidelines
- Inadequate or no recruitment (evaluated after a reasonable amount of time) of participants by the investigator
- Total number of participants included earlier than expected

If the study is prematurely terminated or temporarily suspended, the sponsor shall promptly inform the investigators, the IECs/IRBs, the regulatory authorities, and any contract research organization(s) used in the study of the reason for termination or temporary suspension, as specified by the applicable regulatory requirements. The investigator shall promptly inform the participant and should assure appropriate participant therapy and/or follow-up.

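### In a single-dose study, an investigator-initiated withdrawal for behavioral or compliance reasons ends only observation, and Protocol Section 7.2 does not keep safety follow-up going to Month 6

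*Protocol*

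**What the plan says.** Protocol Section 7.2 gives the investigator a discretionary power: "A participant may be withdrawn at any time at the discretion of the investigator for safety, behavioral, or compliance reasons". The list of primary reasons to be documented in the eCRF includes "Protocol deviation" and "Investigator Decision".

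On data, the same section says: "All data and samples collected up to and including the date of withdrawal of/last contact with the participant will be included" in the analyses. On later follow-up it says: "Investigator will follow participants who are withdrawn from the study due to an AE/SAE/AESI until the event is resolved", stabilized or otherwise explained, or until the participant is lost. It makes no such provision for other withdrawals. Section 8.4.1 adds that investigators have no duty to look actively for AEs or SAEs once participation has ended; an SAE they happen to learn of goes into the medical records, and to the sponsor if considered related.

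Section 4.1 specifies one dose at Visit 1, and Section 7.1 declares discontinuation of intervention not applicable.

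The safety estimand (Protocol Table 8, SAP Table 3) names two intercurrent events: prohibited medication or vaccine, and intercurrent medical conditions. Its handling rule is: "All the data collected for the variable of interest are used regardless of whether the intercurrent event occurs (treatment policy"). SAEs and AESIs are counted to Month 6. SAP Section 4.3.2.1 reports SAEs, pIMDs and fatal SAEs over that period as numbers and percentages of participants in the Exposed Set.

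**The concern.** Withdrawal usually has two parts: stopping treatment and stopping observation. Here there is no treatment left to stop after Day 1, so withdrawing a dosed participant for behavior or compliance costs safety data and spares no exposure.

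A treatment-policy estimand to Month 6 needs data to be collected to Month 6 whatever happens in between. No sentence in either document keeps a participant in safety follow-up after an investigator-initiated withdrawal that is not due to an adverse event. Where one is due to an adverse event, the duty covers that event and not a later, unrelated SAE.

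Because the SAP reports crude percentages of everyone dosed, a participant who leaves at Day 31 stays in the denominator and counts as event-free for the remaining five months. If those withdrawn have a higher risk than those who stay, the loss is informative and the percentages err downward. This matters most for Part B, whose only purpose is safety and whose Month 6 assessment is merely a contact.

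**Working it through.** **1. The plan's own figures.** Protocol Section 9.5 gives N = 1025 (Cohorts 1 and 3) and probabilities of at least one participant with an event. The formula is 1 − (1 − p)^N.

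| True incidence p | Plan | Recomputed |
|---|---|---|
| 0.1% | 64% | 64.1% |
| 0.2% | 87% | 87.2% |
| 0.3% | at least 95% | 95.4% |

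All three reproduce, with every one of the 1025 fully observed. Section 9.5 states no dropout allowance for safety; its 15% concerns evaluability for the primary objectives in Part A.

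**2. Margin at 0.3%.** The plan says "This probability increases to at least 95% for true AE incidence rates" of 0.3% or more. Solving 1 − 0.997^N = 0.95 gives N = ln(0.05)/ln(0.997) = 997.1, so 998 fully observed participants are needed. The margin is 27: the statement fails if 1025 − 997 = 28 participants (2.7%) contribute nothing. A participant withdrawn at Day 31 loses 150 of 180 days, so (1025 − 997.1)/(150/180) = 33.5, meaning 34 such withdrawals (3.3%).

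**3. Effect on Month 6 endpoints.** The documents give no rate of discretionary withdrawal. I assume all withdrawals fall at Day 31, risk is constant over 180 days, and a fraction w is withdrawn.

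- Share of participants with an SAE that is missed, at equal risk: w × 150/180.
- Effective N: 1025 × (1 − w × 150/180).

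| w (assumed) | Share missed | Effective N | Detection at 0.3% |
|---|---|---|---|
| 1% | 0.8% | 1016 | 95.3% |
| 5% | 4.2% | 982 | 94.8% |
| 10% | 8.3% | 940 | 94.1% |

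**4. If the loss is informative.** Suppose those withdrawn have three times the risk of the *other* participants (an assumption without support in the documents). The share missed is 3w × (150/180) / (1 + 2w). For w = 5% this is 0.125/1.10, about 11%; for w = 1% it is 0.025/1.02, about 2.5%.

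**5. Endpoints not affected.** Solicited events (Days 1 to 4) and unsolicited AEs (30 days) are complete before a Day 31 withdrawal. The primary non-inferiority analysis is not touched by this point.

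**The case against.** The strongest reply is that nothing here is a contradiction. Table 8 speaks of data that were collected, and 7.2 uses everything collected up to withdrawal; both can hold. Withdrawal is not an intercurrent event in Table 8, so what follows it is missing data. That is right, and the point is a gap between the two sections, not a conflict of wording.

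Three stronger readings are tempting, and the documents do not support them.

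- **That sites withdraw people for the estimand's own intercurrent events.** The power is permissive, and no text makes prohibited medication or an intercurrent condition a trigger. The plan leans toward retention: SAP Table 5 codes 1040, 2040 and 2050 remove such participants from the PPS only, and both schedules of activities record medication and intercurrent conditions to Month 6. eDiary non-compliance leads first to contact with the participant, and a missed visit to rescheduling and counseling.
- **That the reason list grants authority to withdraw.** It is an eCRF code list recording why someone left. Deleting codes would only make the disposition data less informative.
- **That early completion of enrollment ends follow-up at a site.** Section 10.1.10 lists "Total number of participants included earlier than expected" among possible reasons for closing a site, but does not say that dosed participants there leave follow-up.

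There are also safeguards. Someone withdrawn because of an SAE is already in the SAE numerator. Section 7.3 seeks vital status, but it is placed under loss to follow-up. The SAP tabulates follow-up time, the percentage with at least 6 months, and withdrawal reasons, so a loss would be seen, though not repaired.

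What remains is that no sentence requires SAE and AESI collection to Month 6 after a discretionary withdrawal not due to an adverse event.

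**Conclusion.** The gap is real and probably small in its effect. Section 7.2 permits an avoidable loss of safety follow-up in a study where withdrawal serves no treatment purpose, and the loss lands in crude percentages that treat unobserved time as event-free.

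The sizes are illustrations, since the withdrawal rate, its timing, constant risk and the risk ratio are all assumed. At equal risk, between 0.8% (1% withdrawn) and about 4% (5% withdrawn) of participants with an SAE by Month 6 would be missed. The fall in detection probability at 0.3%, from 95.4% to about 94.8% in the 5% case, is not by itself a reason to act, and ordinary dropout could do the same. The reason to act is possible informative loss, which a follow-up-time table cannot correct. This is a cheap improvement; it does not show that 7.2 defeats the safety estimand.

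**What to change.** Add to Protocol Section 7.2 that, after dosing, a compliance problem, protocol deviation or investigator decision may stop study procedures such as visits and blood draws, but that SAE, AESI and vital-status collection continues to the Month 6 visit (Part A) or contact (Part B) unless the participant declines, dies or is lost to follow-up.

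Keep the eCRF reason codes, apply them to stopping procedures, and record separately whether safety follow-up continued.

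Reconcile the listing of pregnancy as a withdrawal reason in 7.2 with Section 8.4.6, under which a participant who becomes pregnant may stay in the study and continues to be monitored.

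The cost is protocol wording, one extra disposition item, and a Month 6 contact for a few participants who would otherwise have been closed out.

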7.3. Lost to follow-up

A participant will be considered lost to follow-up if the participant repeatedly fails to return for scheduled visits and is unable to be contacted by the study site.

The following actions must be taken if a participant fails to return to the clinic for a required study visit:

- The site must attempt to contact the participant and reschedule the missed visit as soon as possible, counsel the participant on the importance of maintaining the assigned visit schedule and ascertain whether the participant wishes to and/or should continue in the study.
- Before a participant is deemed lost to follow-up, the investigator or designee must make every effort to regain contact with the participant (where possible, 3 telephone calls, and if necessary, a certified letter to the participant's last known mailing address or local equivalent methods). These contact attempts should be documented in the participant's medical record.
- Should the participant continue to be unreachable, the participant will be considered to have withdrawn from the study.
- Site personnel will attempt to collect the vital status of the participant within legal and ethical boundaries for all participants randomized, including those who did not get study intervention. Public sources may be searched for vital status information. If vital status of the participant is determined as deceased, this will be documented, and the participant will not be considered lost to follow-up. Sponsor personnel will not be involved in any attempts to collect vital status information.

8. STUDY ASSESSMENTS AND PROCEDURES

- Study procedures and their timing are summarized in the SoA in Section 1.3. Protocol waivers or exemptions are not allowed.
- Adherence to the study design requirements, including those specified in the SoA, is essential and required for study conduct.
- Immediate safety concerns should be discussed with the sponsor as soon as they occur or when the study team becomes aware of them. In case of doubts of immediate safety concerns regarding the inclusion of a possible participant, inclusion should be postponed until a decision can be made.
- All screening evaluations must be completed and reviewed to confirm that potential participants meet all eligibility criteria prior to study intervention administration. The investigator will maintain a log of all participants screened. All relevant information, such as confirmation of eligibility and reasons for screening failure will be mentioned in this screening log. Participants who have signed informed consent but are not eligible to proceed should be recorded in the eCRF with a status of 'screen failure'.
- If allowed by country regulation/ethics, study visits may be conducted remotely (by a HHS professional or site's own staff) and/or virtually (secure video conferences, phone calls, or a web portal and/or mobile application), as per the SoA.
- In the event of a significant study-continuity issue (e.g., caused by a pandemic), alternate strategies for participant visits, assessments, study intervention distribution and monitoring may be implemented by the sponsor or the investigator, as per local health authority/ethics requirements.
- The maximum amount of blood collected from each participant in Part A (Cohort 1 and 2) over the duration of the study, related to procedures in this study, will not exceed 45 mL and CCI [REDACTED] Repeat or unscheduled samples may be taken once at every timepoint for technical issues with the samples.
- Study participants may decide to assign a caregiver to help them fulfill the study procedures.
- It is preferred to have all visits on-site. However, during special circumstances (e.g., pandemic, patients for whom the transfer to the clinic has become very difficult), the specific guidance from local public health, if applicable, and other competent authorities regarding the protection of individuals' welfare must be applied and consulted with the sponsor. For the duration of such special circumstances, the following measures may be implemented for enrolled participants:
 - For Part A, Visit 3 may be conducted at the participant's home (by the site staff), if appropriate. Biological sample at Visit 3 may be collected at participant's home. Biological samples should not be collected if they cannot be processed in a timely manner or appropriately stored until the intended use.

CCI [REDACTED]

CCI

- For Parts A and B, if the eDiary device has been provided by GSK it may be transmitted from and to the site by courier service if allowed by local regulations and or collected at home.
- Impact of visits performed outside of the site's location on the PPS for immunogenicity will be determined on a case-by-case basis.

8.1. Administrative baseline procedures

8.1.1. Collection of demographic data

Record demographic data such as year of birth, sex, race*, and ethnicity in the participant's eCRF.

Collection of sex, race and ethnicity data is necessary to assess and monitor the diversity of the trial participants, and to determine if the trial participants are truly representative of the impacted population.

*Differences in the safety and efficacy of certain medical products, including vaccines [Haralambieva, 2013; Pérez-Losada, 2009; Kollmann, 2013] have been observed in racially and ethnically distinct subgroups. These differences may be attributable to intrinsic factors (e.g., genetics, metabolism, elimination), extrinsic factors (e.g., diet, environmental exposure, sociocultural issues), or interactions between these factors. Therefore, both geographic ancestry (race) and ethnicity will be collected for all study participants.

Year of birth is collected to stratify the population and determine the impact of the study intervention by age.

8.1.2. Medical/vaccination history

Obtain the participant's medical/vaccination history by interviewing the participant/parent(s)/LAR(s) and/or review of the participant's medical records. Record any relevant pre-existing conditions, signs and/or symptoms present prior to the study intervention/study start in the eCRF.

Any vaccine administered up to 1 year before study vaccine administration should be recorded in the eCRF with date of vaccination. For history of influenza vaccination, information about the vaccine formulation (e.g., adjuvanted or non-adjuvanted or high-dose) should be recorded.

Administration of *Shingrix* and any COVID-19 vaccine/vaccines (if multiple doses/administrations) at any timepoint (even if longer than 1 year before the study vaccine administration) should be recorded in the eCRF. The date of vaccinations should be collected and recorded in the eCRF.

8.1.3. Measure height and weight

Measure the participant's height and weight and record the values in the eCRF.

8.1.4. Smoking status and smoking exposure history

The smoking status will be collected in the eCRF, differentiating tobacco use (cigarettes, cigars, cigarillos, pipes, etc.) and use of electronic smoking devices (e-cigarettes). Refer to [Definition of Terms](#) for the definitions of current and former smoker.

Smoking exposure history should be recorded as number of years for both current and former smokers. When applicable, the number of years of exposure should be collected separately for tobacco and electronic smoking devices.

All data will be recorded in the participant's eCRF.

8.2. Immunogenicity assessments

Planned timepoints for all immunogenicity assessments are provided in the SoA. Immunogenicity assessments will be performed for participants in Part A only (Cohort 1 and Cohort 2).

Biological samples will be used for research planned in the protocol and for purposes related to the improvement, development and quality assurance of the laboratory tests described in this protocol.

Findings in this or future studies may make it desirable to use samples acquired in this study for research not planned in this protocol. In this case, all participants in countries where this is allowed will be asked to give consent to allow GSK or a contracted partner, to use the samples for further research. The further research will be subject to prior IEC/IRB approval, if required by local legislation.

Information on further research and its rationale can be obtained from GSK.

Sample testing will be done in accordance with the recorded consent of the individual participant/participant's parent(s)/LAR(s).

By default, collected samples will be stored for a maximum of 20 years. This storage period begins when the last participant performs the last study visit. This timeline can be adapted based on local laws, regulations or guidelines requiring different timeframes or procedures. In all cases, the storage period should be aligned with participant's consent. These additional requirements must be formally communicated to, discussed and agreed with GSK.

